2.31 Concomitant Medications

Many patients with BPH take medications for symptom control (e.g., alpha blockers, prostaglandin inhibitors, phosphodiesterase inhibitors, etc.). These medications are known to affect BPH symptom scores and marked changes in medication use could contribute to bias in assessing effect sizes. The consent form will note that changes in medications for BPH should be limited during the study's follow-up period. Concomitant medications are captured using the Concomitant Medication log in the study's EDC system.

The investigator:

- Will remind the patient that changes to BPH-related medications should be minimized.
- Will not increase doses of BPH-related medications unless there is marked subject bother. If the dose of any BPH-related medication is increased, reason for increase will be recorded in the medication log.
- Will not start any new BPH-related medication unless there is marked subject bother. Reason for starting a new medication will be recorded in the medication log.
- May reduce the dose of BPH-related medications if the subject experiences drug side effects (e.g., orthostatic hypotension). Reason for decreasing the dose should be documented in the medication log.

2.32 Subject Termination or Withdrawal

Subjects may be terminated or withdrawn from the study for the following reasons:

- Voluntary withdrawal: the subject voluntarily chooses not to further participate in the study. In this case, the site will ask the subject whether he consents to having a telephone call at 12 months after treatment to assess safety and effectiveness outcomes.
- Subject death.
- Adverse event preventing study participation.
- Loss to follow-up (see below)
- At the discretion of the Principal Investigator, or where the ongoing participation of the subject involves a risk greater than perceived benefit.
- The Sponsor may terminate the study at any time.

If a subject withdraws, the site coordinator will complete a withdrawal CRF page.

2.33 Loss to Follow-Up

A subject will be considered "lost to follow up" and terminated from the study when they can no longer be reached by study staff and have missed study visits. The site must notify the sponsor of subject status and consult with them regarding discontinuation of any study subject prior to ceasing all attempts to contact subject. A subject may only be categorized as LTF if the following is true:

- Failure to complete two consecutive follow up visits (unless the missed visit is the last study visit).
- Documentation of three unsuccessful attempts by the Investigator or his/her designee to contact the subject or next of kin.

2.34 Missed Visits/Subject Accountability

Missing data within this subject cohort is expected to occur at a low rate. All efforts will be used to prevent any data from not being captured. The sites will be instructed to identify and obtain contact information for the primary care giver for the subject. Complete site training and regular monitoring will also help to minimize missing data.

In the clinical study report, the number and proportion of subjects who had each follow-up visit will be presented. Subjects who withdraw from the study will be tabulated with the reasons for the withdrawal.

2.35 Study Termination

The sponsor has the right to discontinue the study at any time for any reason.

2.36 Study Exit

The subject's participation in the study is considered complete at the end of the 36-month visit for roll-in subjects, 60-month visit for randomized subjects, or if the subject withdraws from the study. A study exit form shall be completed.

3 STUDY ENDPOINTS

3.1 Primary Safety Endpoint (already reported)

The primary safety endpoint is the proportion of subjects with adverse events rated as probably or definitely related to the study procedure classified as Clavien-Dindo Grade 2 or higher or any Grade 1 event resulting in persistent disability (e.g. ejaculatory disorder or erectile dysfunction) evidenced through 3 months post treatment. Note that the Clavien-Dindo classification scheme is for grading postoperative complications not events that reflect lack of effective treatment.

The Aquablation group will be declared to be non-inferior to TURP if it can be established that the difference in rates is statistically within the non-inferiority margin of $\delta = 0.10$ (see Statistical Analysis below). If non-inferiority is established, a test for superiority will be conducted. If it can be established that the difference is statistically greater than 0, superiority will also be claimed.

3.2 Primary Effectiveness Endpoint (already reported)

The primary effectiveness endpoint is the IPSS change score from baseline to 6 months. A non-inferiority comparison will be performed using a non-inferiority margin of 4.7 points. If non-inferiority is established, a test for superiority will be conducted. If it can be established that the difference is greater than 0, superiority will also be claimed. Adjustment for interim analysis is described below.

3.3 Additional Endpoint Assessments (already reported)

The following is a list of secondary endpoints intended to support product labeling. Statistical details are provided in another section.

- Reoperation or re-intervention within 6 months. Reoperation means any surgical procedure on the lower urinary tract to treat problems potentially related to BPH. Re-intervention means any invasive procedure (e.g., cystoscopy) to evaluate problems potentially related to BPH. Re-intervention excludes TRUS and urodynamics evaluations required by the study during follow-up.
- Evaluation of the proportion of sexually active subjects reporting a worsening of sexual function through 6 months on either the IIEF-15 or the MSHQ-EjD questionnaires
- Evaluation of the proportion of subjects meeting a composite of serious device or procedure related events defined as MAUE through 6 months
- Length of hospital stay (days) in the treatment groups
- Length of operative time (minutes) in the treatment groups, defined as time from pre-treatment visualization to insertion of indwelling catheter (IDC).
- Length of resection time (minutes) in the treatment groups, defined as start of first pedal activation to end of last pedal use for either Aquablation or TURP.

The following objectives are pre-specified but are not intended to support product labeling:

- Evaluation of proportion of subjects with Clavien-Dindo classification of Grade 2 or higher or any Grade 1 with persistent disability (e.g. ejaculatory disorder or erectile dysfunction) at 30 days, 6 months, and 1 year
- Evaluation of the proportion of subjects with Dysuria through 30 days
- Duration of catheterization (hours)
- Change in hemoglobin (gm/dl) at discharge from baseline
- Reoperation or Re-intervention within 30 days, 12 months, 24 months 36 months, 48 months, and 60 months
- Changes in the proportion of subjects using medications for BPH symptoms at month 6. An additional analysis of change in total daily dose of BPH-specific medications (e.g., alpha blockers, prostaglandin inhibitors, phosphodiesterase inhibitors, etc.) at month 6 will be performed.
- IPSS score at baseline, and 7 days, 1, 3, 6, 12, 24, 36 months, 48 months, and 60 months
- IPSS-QoL at baseline, and 7 days, 1, 3, 6, 12, 24, 36 months, 48 months, and 60 months
- Qmax at baseline, 1, 3, 6, 12, 24, 36 months and 60 months
- PVR at baseline, 1, 3, 6, 12, 24, 36 months and 60 months
- Outcome of device/procedure related serious adverse events
- Pain & dysuria score at post-op, 7, 30 days, and 3 months
- EQ-5D at baseline, and 7 days, 1, 3, 6, 12, 24 and 36 months
- ISI at baseline, at post-op, 7 days, 1, 3, and 6 months
- IIEF-15 at baseline, and 7 days, 1, 3, 6, 12, 24, 36 months and 60 months
- MSHQ-EjD at baseline, 7 days, 1, 3, 6, 12, 24, 36 months and 60 months
- WPAI:US at baseline, 7 days, 1, 3, 6, 12, 24 and 36 months
- Pdet@Qmax at baseline and 6 months
- Change in categorization, by treatment group, of subjects from obstructed to unobstructed or unobstructed to obstructed. The determination of “obstructed” and “unobstructed” is based on Chapple [20]
- Use of cautery immediately post Aquablation. Cautery use will be assessed as minutes from cautery start to stop and total amount of “on time”.
- Number of subjects in whom re-catheterization was needed between discharge after the index procedure and month 3. Re-catheterization is defined as the need to place a urinary catheter in the bladder for symptoms related to BPH. This excludes re-catheterization for study purposes or for purposes unrelated to LUTS.
- Amount of irrigation fluid used intraoperatively (liters)
- Number of subjects in whom postoperative irrigation started
- Amount of Fluid used postoperatively (liters)
- Duration of postoperative irrigation (hours)
- Subset analyses of the following variables by treatment and baseline IPSS scores of < 20 and ≥ 20 , as well as by treatment and baseline prostate size of $< 45g$ and $\geq 45g$:
 - IPSS score at baselines, and 7 days, 1, 3, 6, 12, 24 and 36 months
 - IPSS-QoL at baseline, and 7 days, 1, 3, 6, 12, 24 and 36 months
 - Qmax at baseline, 1, 3, 6, 12, 24 and 36 months
 - PVR at baseline, 1, 3, 6, 12, 24 and 36 months
 - Operative time (minutes)
 - Resection time (minutes)
- Evaluation of proportion of subjects with Clavien-Dindo classification of Grade 2 or higher or any Grade 1 with persistent disability (e.g. ejaculatory disorder or erectile dysfunction) at 30 days, 3 months, 6 months, and 1 year

4 STATISTICAL CONSIDERATIONS

4.1 Primary Statistical Objective

The primary objective of this study is to demonstrate non-inferiority in the safety and effectiveness of the Aquablation and TURP in the treatment of BPH in men 45 - 80 years of age. Both the primary safety and primary effectiveness endpoints must be met in order to consider the Study a success.

4.2 Primary Effectiveness Endpoint Calculation

The primary effectiveness hypothesis is a non-inferiority comparison of the mean change in IPSS score from baseline to 6 months across groups using a non-inferiority margin of 4.7 points. This type of comparison is consistent with FDA guidance [14].

For the primary effectiveness endpoint, the null hypothesis is that the mean IPSS change score for Aquablation is inferior to that for TURP, using a non-inferiority margin of 4.7 points.

The alternative hypothesis is that the mean IPSS change score for Aquablation is non-inferior to TURP, using a non-inferiority margin of 4.7 points.

These hypothesis statements are written as follows:

$$H_0: \mu_C - \mu_T \leq -\delta$$

$$H_A: \mu_C - \mu_T > -\delta$$

where μ_T and μ_C represent the mean changes in IPSS (from baseline to 6 months) for the treatment and control groups, respectively. Negative changes from baseline represent patient improvement under this design. The pre-specified non-inferiority margin (δ) is 4.7 points. The hypothesis will be tested with one-sided overall type I error controlled at 0.025 using an O'Brien-Fleming-type spending function to account for possible early stopping with a single interim analysis when all subjects are through 3 months of follow-up.

Aquablation will be declared non-inferior to TURP if it can be established that the difference in change in IPSS score between the two groups is within the non-inferiority margin of $\delta = 4.7$ points. If non-inferiority is established, a test for superiority will be conducted. If it can be established that the mean difference is statistically greater than 0 points (i.e. $\mu_T > \mu_C$), superiority will also be claimed.

Justification for 4.7 point Non-Inferiority Margin (NIM): As outlined in the BPH guidance document,¹ for non-inferiority studies, the hypothesis should incorporate a non-inferiority delta level that reflects a maximum tolerable difference that is “clinically insignificant” (i.e., “not clinically meaningful”) in the analysis of the primary endpoint. Larger values of the non-inferiority delta level are usually supported by demonstrating significant benefits in the safety of the investigational device. In addition, the draft FDA guidance for non-inferiority trials advises that the non-inferiority margin must be no larger than the entire assumed treatment effect of the active control (i.e. TURP) and should reasonably rule out an effect in a placebo arm had there been one [20].

Barry et al², further corroborated by Roehrborn et al³, evaluated the minimum change from baseline in symptom score required for patient perception on benefit and demonstrated that the magnitude of improvement in symptom score required for patient perception of change was correlated with the subjects baseline score. Subjects with a higher score at baseline require a greater decrease in symptom score to obtain the same level of satisfaction when compared to subjects with a lower symptom score at baseline (Table 6 below).

¹ <http://www.fda.gov/downloads/medicaldevices/deviceregulationandguidance/guidancedocuments/ucm223664.pdf>

² Barry, MJ, Willifred WO, Chang Y, et al., **Benign prostatic hyperplasia specific health status measures in clinical research: How much change in the American Urological Association Symptom Index and the Benign Prostatic Hyperplasia Impact Index is perceptible to patients.** J Urol, 1995, 154:1770-1774.

³ Roehrborn, Claus G.; Wilson, Timothy H.; Black, Libby K. **Quantifying the Contribution of symptom improvement to satisfaction of men with moderate to severe benign prostatic hyperplasia: 4-year data from the CombAT trial.** Journal of Urology, 2012. Vol. 187, No. 5, p. 1732-1738.

Table 6. Mean absolute changes in AUA symptom and BPH impact index scores for each level of self-rated global improvement for subjects with lower versus higher baseline scores²

Pt Assessment of Improvement	Mean Absolute Change +/- SEM (No Patients) in AUA Symptom Index	
	Lower Baseline Scores*	Higher Baseline Scores*
Marked	-7.4 ± 0.29 (183)	-16.3 ± 0.76 (40)
Moderate	-4.0 ± 0.29 (227)	-8.7 ± 0.62 (70)
Slight	-1.9 ± 0.29 (252)	-6.1 ± 0.54 (95)
None	-0.2 ± 0.35 (184)	-2.0 ± 0.62 (69)
Worse	+3.3 ± 1.09 (17)	+1.2 ± 1.79 (7)

* Lower baseline score 8 to 19 points, higher baseline score 20 to 35 points.

Given that this perception of meaningful change is variable relative to baseline IPSS, the appropriate NIM for the WATER trial is derived from the expected baseline of the study population and the data from the Barry study regarding Mean Absolute Change in AUA Symptom Index required for slight improvement (lower baseline scores 8-19 points, AUA-SI change of 1.9 points; higher baseline scores 20-35 points, AUA-SI change of 6.1 points). Data available from prior studies (Procept and other BPH device trials) supports that a reasonably conservative estimate of distribution of subjects between the lower baseline scores (12-19) and higher baseline scores (20 and above) is 33% lower baseline and 67% higher baseline. Applying this distribution of baseline symptom score to the data from Barry et al, we calculate the appropriate NIM for the WATER study to be 4.7 points (1/3*1.9 + 2/3*6.1).

The treatment effect observed in SHAM controlled trials for other devices is approximately 6 points [21] [22]. In addition, the placebo control arm rates for drug studies range from 2-5 point reduction in symptoms [23]. Provided the lower bound of the one-sided 97.5% confidence interval of the difference between treatment groups exceeds 6 points, we can reasonably rule out the effect that might be associated with a drug placebo or a SHAM procedure. The change in IPSS score from baseline expected with the proposed active control TURP is estimated at 15 points [24], [25], [26], [27]. A symptom improvement of approximately 1.5 points less for PROCEPT with a lower bound of a one-sided 97.5% confidence interval of 4.7 points less for PROCEPT than TURP (e.g. an Aquablation improvement in IPSS of >10 points including the lower bound of the one-sided 97.5% confidence interval) is clinically meaningful and is in line with the treatment effect reported in trials for other approved devices (improvement of 6-13 pts for TUMT and UroLift [21], [22], [28], [29]).

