4.4 Sample Size Considerations and Statistical Analyses

The WATER Study is designed as a prospective, randomized, blinded, controlled trial to demonstrate non-inferiority of the AQUABEAM System to TURP with respect to symptom improvement at 6 months. The WATER Study is designed in accordance with FDA's "Guidance for Non-Clinical and Clinical Investigation of Devices Used for the Treatment of Prostatic Hyperplasia (BPH)," published August 17, 2010.

Subjects will be randomly assigned in a 2:1 ratio to treatment with Aquablation or to treatment with TURP. The Primary Effectiveness Endpoint for this clinical trial is change in IPSS from baseline to 6-month evaluation.

Minimum enrollment (N_{\min}) in the WATER trial is 177 subjects (118 Aquablation and 59 TURP) to power at 80% for possible demonstration of superiority for the safety endpoint under an assumption of an endpoint rate of 65% in TURP and 40% in Aquablation, while including a 12% lost to follow-up rate (i.e., 156 evaluable subjects). The primary safety endpoint with 156 subjects evaluable displays over 99% power at a one-sided alpha level of 0.025 to demonstrate non-inferiority within a margin of 10% under an assumption of a true rate of events in the Aquablation group of 40% and expected rate of 65% in the TURP group.

Under an assumption of an effectiveness NIM of 4.7 points and a treatment effect of -1.5 points (i.e., mean change score in Aquablation is 1.5 points lower than TURP) with a standard deviation of 6 points, the sample size of 156 evaluable subjects provides more than 80% power in a test of non-inferiority for the primary effectiveness endpoint.

The trial will utilize a group sequential design with a single interim look and will incorporate a sample size re-estimation (SSR) at the time of the interim look based on promise for superiority on effectiveness. Methods for the SSR have been described in detail [30] [31].

An O'Brien-Fleming (OBF) alpha-spending function will be employed to control for type I error rate on the primary effectiveness endpoint. The maximum enrollment being considered is 270 total enrolled ($N_{\max} = 1.5$ times N_{\min}).

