where μ_T and μ_C is the average length of stay in days in the treatment and control groups, respectively. Statistical summaries will include means, medians, and standard deviation, as well as 95% confidence intervals. A t-test for superiority will be performed to test the hypothesis that μ_T is significantly less than μ_C .

- Evaluation of the mean length of operative time in the treatment groups. The following hypothesis will be tested:

$$H: \mu_T - \mu_C > 0$$

where μ_T and μ_C is the average operative time in minutes in the treatment and control groups, respectively. Statistical summaries will include means, medians, and standard deviation, as well as 95% confidence intervals. A t-test for superiority will be performed to test the hypothesis that μ_T is significantly less than μ_C .

- Evaluation of the mean length of resection time in the treatment groups. The following hypothesis will be tested:

$$H: \mu_T - \mu_C > 0$$

where μ_T and μ_C is the average operative time in minutes in the treatment and control groups, respectively. Statistical summaries will include means, medians, and standard deviation, as well as 95% confidence intervals. A t-test for superiority will be performed to test the hypothesis that μ_T is significantly less than μ_C .

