## 5.2 Primary Effectiveness Endpoint

The primary effectiveness endpoint is the IPSS change score from baseline to 6 months. IPSS is an accepted and commonly used measure for symptom severity in BPH. IPSS varies from 0 (no symptoms) to 35 (maximal symptoms).

The difference in mean change scores will be calculated as  $D=D_A-D_T$ , where  $D_x$  signifies mean improvement from baseline, expressed as a positive number.  $D$  is the difference improvement; thus if the improvement is 14 points in A and 15 points in T, the difference  $D = -1$  point. The primary hypothesis is that of non-inferiority of 6-month change scores:

$$H_{0,E,N}: D=D_A-D_T \leq \text{NIM}$$

$$H_{A,E,N}: D=D_A-D_T > \text{NIM}$$

For these hypotheses, NIM is expressed as a negative number (e.g., -5 points). If non-inferiority is concluded, an additional test will be performed for statistical superiority:

$$H_{0,E,S}: D=D_A-D_T \leq 0$$

$$H_{A,E,S}: D=D_A-D_T > 0$$

The same notation is used for the last subscript: N = non-inferiority and S = superiority. Therefore, the 4 effectiveness hypotheses are:

- Null for non-inferiority
- Alternative for non-inferiority
- Null for superiority
- Alternative for superiority

A 2-sided 95% confidence interval for the difference in means will be used to test for non-inferiority. Non-inferiority will be declared if the entire 2-sided 95% CI is greater than the NIM (where NIM is expressed as a negative number). A gate-keeping strategy is used such that if the non-inferiority test is positive, a superiority test will be performed. A 2-sided  $(1-\alpha)\%$  confidence interval will be used to test for superiority. Superiority will be declared if the entire 2-sided 95% CI is greater than 0%. The sample size is fixed for the non-inferiority trial, but the sample size may increase (described below). For this reason, a multiplicity adjustment is required for the superiority analysis. Critical values will be chosen to ensure Type I error control.

The study will be deemed a non-inferiority success if both the safety and effectiveness primary endpoint null hypotheses are rejected. Additional analyses for the primary effectiveness endpoint will be performed using general linear models that incorporate potential predictors of IPSS change scores (e.g., baseline IPSS) as covariates. Subgroup analysis is described below.

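### Protocol 4.2 glosses effectiveness superiority as μT > μC, the reverse of its own sign convention, its own contrast and SAP 5.2

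*Protocol*

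**What the plan says.** **Protocol 4.2.** μT and μC "represent the mean changes in IPSS (from baseline to 6 months) for the treatment and control groups, respectively", and "Negative changes from baseline represent patient improvement under this design". The alternative for non-inferiority is μC − μT > −δ, and "The pre-specified non-inferiority margin (δ) is 4.7 points". Superiority is tested only after non-inferiority is established: "If it can be established that the mean difference is statistically greater than 0 points", explained in brackets as μT > μC, superiority is claimed as well.

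**Protocol 1.2 and 3.2.** Both repeat the rule as a difference greater than 0, without saying which arm is subtracted from which. The bracket in 4.2 is therefore the only explicit direction that the protocol gives for this claim.

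**SAP 5.2.** The SAP uses the opposite sign. Its D for each arm "signifies mean improvement from baseline, expressed as a positive number", and D = D_A − D_T. Superiority is D > 0. Its worked example (14 points in A and 15 in T give D = −1) leaves no doubt that positive D favours Aquablation.

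**Related notation.** Protocol 4.4 describes the planning effect of −1.5 points as "mean change score in Aquablation is 1.5 points lower than TURP". Protocol 4.6 prints an unlabelled H: μT − μC > 0 for hospital stay, operative time and resection time. For each it then says "A t-test for superiority will be performed to test the hypothesis that" μT is below μC.

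**The concern.** With negative change meaning improvement, μT > μC says that the IPSS fell less after Aquablation than after TURP. The bracket therefore describes TURP doing better, yet it is given as the condition for claiming that Aquablation is superior. It also contradicts the contrast set out just above it, where a larger μC − μT favours Aquablation.

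This is the written decision rule for a primary claim. Protocol 4.4 also bases its conditional power for superiority, and so the possible sample-size increase, on that claim. A reader with both documents finds opposite directions for the same claim.

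**Working it through.** **Direction, by algebra.** On the contrast in 4.2, superiority is the non-inferiority alternative with the margin set to 0: μC − μT > 0, which is μT < μC. Protocol 4.4 takes a planning effect of 1.5 points and 4.2 expects a TURP improvement of about 15 points. Two cases:

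- TURP −15, Aquablation −13.5: μT > μC holds, although Aquablation improved 1.5 points less.
- TURP −15, Aquablation −16.5: μT > μC fails, although Aquablation improved 1.5 points more.

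SAP 5.2 gives D = −1.5 and D = +1.5 for these cases and so classifies both correctly.

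**Inputs for the size** (Protocol 4.2 and 4.4): margin 4.7, SD 6, one-sided α 0.025, 2:1 allocation, 12% loss to follow-up. 177 × 0.88 = 155.8, so 156 evaluable, split 104 and 52. The normal approximation is used and the interim adjustment is ignored.

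SE = 6 × √(1/104 + 1/52) = 1.019. Critical distance = 1.96 × 1.019 = 2.00.

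**The plan's own figure first.** Non-inferiority power if Aquablation improves 1.5 points less: Φ((4.7 − 1.5)/1.019 − 1.96) = Φ(1.18) = 88.1% (87.7% by noncentral t). The stated figure of more than 80% is reproduced. If 1.5 points better instead: Φ(6.2/1.019 − 1.96) = Φ(4.12), above 99.9%. The statement is true on either reading of the planning effect.

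**The literal rule, after non-inferiority.** Let d be the observed μT − μC, so positive d means that Aquablation is worse.

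- Non-inferiority needs d + 2.00 < 4.7, so d < 2.70.
- The bracket needs d − 2.00 > 0, so d > 2.00.
- Together, 2.00 < d < 2.70: Aquablation is significantly worse than TURP but within the margin.

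If Aquablation is truly 1.5 points worse: Φ((2.70 − 1.5)/1.019) − Φ((2.00 − 1.5)/1.019) = Φ(1.18) − Φ(0.49) = 19.4%.

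The same calculation for other true effects:

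| True position of Aquablation | Superiority claimed, bracket read literally after non-inferiority | Superiority claimed, μT < μC |
|---|---|---|
| 3 points worse | 22.3% | below 0.01% |
| 1.5 points worse | 19.4% | 0.03% |
| Equal | 2.1% | 2.5% |
| 1.5 points better | 0.03% | 31.3% |
| 3 points better | below 0.01% | 83.7% |

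In the last column the non-inferiority step removes nothing, because a result that excludes 0 in Aquablation's favour also excludes the margin.

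**The case against.** The strongest reply is that only a bracket is wrong. The words before it are correct on the contrast μC − μT, and 1.2 and 3.2 give the rule without the bracket. Protocol 4.4 leaves full statistical detail to the SAP, whose superiority hypotheses are explicit and correctly oriented, so an analyst following the SAP would not make the wrong claim. Revision H is a post-market follow-up revision, and section 3 marks the endpoints as already reported, so no pending primary decision depends on the wording. All of this stands and lowers the severity. It does not remove the contradiction, because nothing else in the protocol states the direction.

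Four stronger readings are tempting, and the documents do not support them:

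- **A 31% chance of a wrong claim.** Φ(1.5/1.019 − 1.96) = 31.3% is the bracket taken alone. The protocol tests superiority only after non-inferiority, which brings it to 19.4%.
- **The three time endpoints reward the worse arm.** The printed H lines in 4.6 look reversed, since the re-operation endpoint there uses the same unlabelled H for an alternative. But for each time endpoint the text says that the test is for μT below μC, so the stated test direction is right.
- **It is unclear which scenario the power refers to.** Read by the convention in 4.2, a lower change score would mean better. But the margin justification in 4.2 speaks of about 1.5 points less improvement with the investigational device. SAP 5.5 gives −1.5, and under SAP 5.2 a negative value means less improvement with Aquablation. The intent is clear and only the phrase in 4.4 is loose.
- **The sign conventions themselves conflict.** Two conventions are not an error when each is applied consistently. The fault is one inequality that breaks the protocol's own.

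**Conclusion.** The superiority condition as spelled out in Protocol 4.2 is reversed. It contradicts the section's sign convention, its contrast and SAP 5.2. Read literally after non-inferiority, it would claim superiority about 19% of the time when Aquablation is truly 1.5 points worse and almost never when it is 1.5 points better. Those figures rest on the planning SD of 6, on 104 and 52 evaluable subjects and on unadjusted one-sided 0.025 tests. They describe the wording, and the documents give no sign that the reported analysis followed it.

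The notation in 4.4 and 4.6 is a lesser matter of tidying. Severity is minor to moderate: a clear error in the rule for a primary claim, limited in practice by a correct SAP and an endpoint already reported.

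**What to change.** 1. **Protocol 4.2:** state that superiority is claimed if μC − μT is statistically greater than 0 (i.e. μT < μC). This matches SAP 5.2.
2. **Clarification note:** confirm that the reported effectiveness superiority analysis used the SAP direction, D_A − D_T > 0.
3. **Protocol 4.6, clean-up:** label the three time-endpoint hypotheses as Ha: μT − μC < 0, to agree with the accompanying text. This does not settle a separate conflict on hospital stay: the protocol plans a t-test for superiority, while SAP section 6 plans proportional odds regression with a half-day margin. That needs its own reconciliation.
4. **Protocol 4.4, clean-up:** restate the planning effect as an Aquablation improvement 1.5 points smaller than that with TURP.

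The cost is protocol wording and one check of the completed analysis. No sample size, margin or power figure changes.
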